#### 11.6. Post-Study Reporting Requirements

Although such information may not be routinely sought or collected by the Sponsor, SAEs that occur after the subject has completed a clinical study may be reported. Such cases will be evaluated for expedited reporting.

# 11.7. Regulatory Reporting of Adverse Events

The Sponsor will have final determination of when an event must be reported to the relevant regulatory authorities and is responsible for notifying the relevant regulatory authorities of certain events. The Investigator will report all SAEs that occur at his/her site to the IRB per the site's IRB regulations. AEs will be reported to regulatory authorities in compliance with 21 CFR 312.32, local and regional law and established guidance by the Sponsor or its designee. The format of the reports will be dictated by the local and regional requirements.

Galera Therapeutics, Inc.

Version: Amendment 4

Investigators will also be notified of all unexpected, serious, drug-related events (7/15-Day Safety Reports) that occur during the clinical study. Each site is responsible for notifying its IRB/IEC/REB of these additional SAEs in accordance with local or central IRB/IEC/REB procedures. Copies of each report will be kept in the Investigator's files and adequate documentation will be provided to the Sponsor including documentation that the IRB/IEC/REB was notified of each safety report.

# 11.8. Pregnancy

The risks of treatment with GC4419 during pregnancy have not been evaluated. Male subjects and female subjects of childbearing potential who engage in sexual intercourse should use a barrier method of contraception throughout the study and for 30 days (females) or 90 days (males) following the last dose of GC4419/Placebo.

# 11.8.1. Time Period for Collecting Pregnancy Information

As permitted by IRB/EC/REB policies, any pregnancy that occurs from the first dose of GC4419/Placebo up to 30 days after last dose should be reported using the appropriate form within 2 weeks of learning of the subject's pregnancy. The subject will be followed throughout the course of the pregnancy. Generally, follow-up will be no longer than 6 to 8 weeks following the estimated delivery date. Any premature termination of the pregnancy should be reported. If a pregnancy is identified outside the 30 days after last dose, the Investigator may report using clinical judgment.

## 11.8.2. Action to be Taken if Pregnancy Occurs in a Female Partner of a Male Subject

The Investigator will attempt to collect pregnancy information on any female partner of a male study subject who becomes pregnant while the male partner is participating in this study. The Investigator will record pregnancy information on the appropriate form and submit it to the Sponsor within 2 weeks of learning of the partner's pregnancy. The partner will also be followed to determine the outcome of the pregnancy. Information on the status of the mother and child will be forwarded to the Sponsor. Generally, follow-up will be no longer than 6 to 8 weeks following the estimated delivery date. Any premature termination of the pregnancy will be reported. If a pregnancy is identified outside the 30 days after last dose, the Investigator may report using clinical judgment.

## 12. STATISTICS

#### 12.1. General Considerations

A separate Statistical Analysis Plan will provide technical details of the statistical analyses to be performed, in addition to the specifications in this protocol. In the event of discrepancies between the protocol and the Statistical Analysis Plan, the latter will control the analyses performed.

Galera Therapeutics, Inc.

Version: Amendment 4

All statistical analyses will be conducted with the SAS® software package version 9.2 or higher.

#### 12.1.1. Randomization and Stratification

Eligible subjects will be randomized 3:2 to the two treatment arms. Randomization will be stratified by:

Assigned cisplatin schedule (q3 weeks or weekly).

Post-operative vs. definitive treatment

# 12.1.2. Treatment of Subjects Affected by Sponsor Dosing Suspension

On April 28, 2019, the Sponsor voluntarily suspended dosing in the trial following observation of fine particulate matter in two lots of clinical Drug Product (DP) at the 9-month stability test point. Subsequent analysis found that these two DP lots remained within specifications, and the adverse event profile in subjects who had received GC4419 from them was not different from observations in subjects who had received GC4419 from unaffected DP lots. Particulates had neither been observed in the DP lots in question at prior test points (3 and 6 months), nor in prior DP lots. The FDA's Division of Dermatology and Dental Products subsequently placed the IND on full clinical hold on July 15, 2019. The Sponsor submitted a Complete Response to Clinical Hold on August 7, 2019, and FDA removed the clinical hold on August 30, 2019. No subjects were enrolled to the study or received study drug from April 28, 2019 until after the removal of the clinical hold.

The "intent to treat" (ITT) population is defined to consist of all randomized subjects who receive at least one dose of blinded GC4419 or placebo. However, when the Sponsor suspended dosing, 28 subjects were in the course of receiving GC4419 or placebo. These 28 subjects will be excluded from the ITT analysis on the ground that their participation does not reflect an adequate test of the hypothesized effects of the experimental agent.

## 12.2. Sample Size

Approximately 450 total subjects (270 GC4419:180 Placebo) will be enrolled from investigational sites in the United States and Canada to obtain approximately 400 ITT subjects (240 GC4419:160 Placebo). The proposed ITT sample size of 400 assumes that 10% will discontinue early, yielding approximately 216 subjects in the experimental arm and approximately 144 in the Placebo arm who will complete their IMRT course.

With 144 subjects in the control arm and 216 subjects in the experimental arm, the study will have approximately 95% power to detect a relative reduction in incidence of severe OM throughout the treatment period in the experimental arm of approximately 34% compared to Placebo (i.e., 43% incidence for GC4419 vs 65% for Placebo).

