#### **Statistical Methods:**

Approximately 450 subjects will be enrolled (270 GC4419:180 Placebo) to obtain approximately 400 Intent-to-Treat (ITT) subjects (240 GC4419:160 Placebo). The proposed ITT sample size of 400 assumes that 10% will discontinue early, yielding approximately 216 subjects in the experimental arm and approximately 144 in the Placebo arm who will complete their IMRT course. The study will have approximately 95% power to detect a relative reduction in incidence of severe OM throughout the study treatment period in the experimental arm of approximately 34% compared to Placebo (43% incidence for GC4419 vs 65% for Placebo).

Safety and efficacy will be assessed on the ITT population consisting of all randomized subjects who receive at least one dose of GC4419/Placebo, excluding the 28 subjects whose dosing was interrupted due to the Sponsor's dosing suspension decision.

Analysis of incidence/proportion endpoints will use the Cochran-Mantel-Haenszel (CMH) test stratified by the randomization factors as entered at treatment assignment. The study hypothesis for the primary endpoint will be tested at a 2-sided Type 1 error rate of 0.05.

To control the overall Type 1 error at 0.05, the primary endpoint will first be tested at a two-sided 0.05 level. If the primary endpoint result is significant at this level, then Holm-Bonferroni multiplicity testing will be conducted on the following proposed secondary endpoints applying a familywise two-sided alpha of 0.05:

- incidence of Grade 4 OM during the Study Treatment Period;
- total number of SOM days (per subject) during the OM Observation Period for the entire study population; and
- total number of days of Grade 4 OM (per subject) during the OM Observation Period for the entire study population.

Efficacy analyses will be stratified by the randomization strata:

Cisplatin schedule (weekly vs q3weekly)

Post-operative vs definitive treatment.

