# 12.5. Primary Efficacy Analysis

SOM incidence (i.e., the proportion of subjects with SOM) during the Study Treatment Period will be compared between the GC4419 and Placebo arms by the Cochran-Mantel-Haenszel (CMH) test at a 2-sided Type 1 error rate of 0.05.

Efficacy analyses will be stratified by the factors used in randomization, namely post-operative vs. definitive treatment and planned chemotherapy schedule.

Details of the primary efficacy analysis will be included in the Statistical Analysis Plan.

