#### 12.5.1. Multiplicity

To control the overall Type 1 error at 0.05, the primary endpoint will first be tested at a two-sided 0.05 level. If the primary endpoint result is significant at this level, then Holm-Bonferroni multiplicity testing will be conducted on the following proposed secondary endpoints applying a familywise two-sided alpha of 0.05:

- incidence of Grade 4 OM during the Study Treatment Period:
- total number of SOM days (per subject) during the OM Observation Period for the entire study population; and

• total number of days of Grade 4 OM (per subject) during the OM Observation Period for the entire study population.

Galera Therapeutics, Inc.

Version: Amendment 4

Further details regarding multiplicity testing will be included in the Statistical Analysis Plan.

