# 12.9. Interim Analysis

No interim efficacy analysis is planned.

An independent Data Monitoring Committee (DMC) will perform periodic unblinded safety reviews while subjects in the study receive GC4419/Placebo.

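### The stated power of about 95% does not follow from the plan's own inputs, which give about 98.6% at two-sided 0.05; correct the figure or state its basis.

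*Combined protocol and SAP*

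**What the plan says.** Section 12.2 starts from about 450 enrolled, of whom about 400 form the ITT set (240 GC4419, 160 Placebo). It allows for 10% early discontinuation, leaving 216 and 144 who complete IMRT. The power sentence is tied to those completers: "With 144 subjects in the control arm and 216 subjects in the experimental arm, the study will have approximately 95% power". The effect to be detected is a relative reduction of "approximately 34% compared to Placebo (i.e., 43% incidence for GC4419 vs 65% for Placebo").

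The synopsis (Statistical Methods) repeats the figure: "The study will have approximately 95% power to detect a relative reduction in incidence of severe OM".

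Section 12.2 names no significance level. The level appears in three other places, always with the same value:

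- Synopsis, Statistical Methods: "The study hypothesis for the primary endpoint will be tested at a 2-sided Type 1 error rate of 0.05".
- Section 12.5: the comparison uses the "Cochran-Mantel-Haenszel (CMH) test at a 2-sided Type 1 error rate of 0.05".
- Section 12.5.1: "the primary endpoint will first be tested at a two-sided 0.05 level".

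Section 12.9 adds: "No interim efficacy analysis is planned". Section 12.1 says "A separate Statistical Analysis Plan will provide technical details of the statistical analyses to be performed"; that separate SAP is not in the text supplied for review.

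**The concern.** A power statement should be reproducible from the sample sizes, event rates, test and alpha that the plan gives. Here all four are available, and the primary endpoint receives the whole of the two-sided 0.05: it is tested before the secondary endpoints and there is no interim efficacy look. Nothing in the text would lower the power to 95%.

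Little is at stake for the validity of the trial, because the stated figure is too low rather than too high. What suffers is the record of the design. In Appendix 8 the sponsor gives statistical power as one of two reasons for raising enrolment in Amendment 4, the other being the safety database. A reader who checks the figure finds that it does not reproduce. That reader cannot tell whether it is a slip or was computed against a stricter criterion that the protocol does not disclose.

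**Working it through.** **Inputs.** n₁ = 216 (GC4419), n₂ = 144 (Placebo), p₁ = 0.43, p₂ = 0.65 (Section 12.2). Two-sided α = 0.05, so z = 1.960 (synopsis, Sections 12.5 and 12.5.1). No alpha is spent on interim looks (Section 12.9).

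**Figures in Section 12.2 that do reproduce.** 240 × 0.9 = 216; 160 × 0.9 = 144; (65 − 43)/65 = 33.8%, stated as about 34%.

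**Power, normal approximation with pooled null variance.**

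- Pooled rate: p̄ = (216 × 0.43 + 144 × 0.65)/360 = 0.518.
- Null SE: √[0.518 × 0.482 × (1/216 + 1/144)] = 0.05376.
- Alternative SE: √[0.43 × 0.57/216 + 0.65 × 0.35/144] = 0.05210.
- Power = Φ[(0.22 − 1.960 × 0.05376)/0.05210] = Φ(2.200) = 0.986.

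**Other methods, same inputs.**

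| Method | Power |
|---|---|
| Pooled normal | 0.9861 |
| Unpooled normal: Φ(0.22/0.05210 − 1.960) = Φ(2.263) | 0.9882 |
| Arcsine | 0.9853 |
| Continuity-corrected | 0.9817 |
| Exact enumeration of the Mantel-Haenszel statistic | 0.9856 (0.9805 with continuity correction) |
| Fisher exact | 0.981 to 0.982, depending on how the two-sided p-value is defined |
| Stratified CMH, simulated, four equal strata | 0.9861 |
| Stratified CMH, simulated, strata of 40/30/20/10% | 0.9859 |

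The stratum sizes in the last two rows are assumptions, with 43% vs 65% applied in every stratum. The range is 98.1% to 98.8%, and the stated 95% is not reproduced by any method.

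**What 95% power would correspond to.**

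- Sample size at 43% vs 65% and 3:2 allocation, pooled: N = [(1.960 × √1.0403 + 1.645 × √0.97725)/0.22]² = 271.5, so 272 (163 and 109). Here 1.0403 = 0.518 × 0.482 × (1/0.6 + 1/0.4) and 0.97725 = 0.43 × 0.57/0.6 + 0.65 × 0.35/0.4. Other methods give 262 (unpooled), 273 (arcsine) and 290 (continuity-corrected).
- Effect at 216/144 against 65%: a GC4419 rate of 45.9% (pooled) or 46.2% (unpooled), rather than 43%.

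**Could another reading give 95%?** The settings below are not stated as the basis of the 95%; they show the range. All use the pooled formula unless noted.

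| Setting | Power |
|---|---|
| 240/160, rates undiluted, α 0.05 | 0.9924 |
| 240/160, the 10% GC4419 non-completers at the Placebo rate (0.9 × 0.43 + 0.1 × 0.65 = 0.452), α 0.05 | 0.976 |
| 360 completers less 28, α 0.05 | 0.979 |
| 216/144, two-sided α 0.025 | 0.972 |
| 216/144, two-sided α 0.01 | 0.9412 pooled, 0.9502 unpooled |
| 240/160, GC4419 non-completers at 80%, Placebo 65%, α 0.05 | 0.9535 |
| 240/160, GC4419 non-completers at 65%, Placebo non-completers at 50%, α 0.05 | 0.9524 |
| 240/160, all GC4419 non-completers counted as SOM, Placebo 65%, α 0.05 | 0.8997 |

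With 216/144 the pooled formula gives exactly 95% at a two-sided alpha of about 0.0125.

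**The case against.** The best counter-argument is that 95% may be a correct figure whose basis was left out. At two-sided 0.01 the same inputs give 94.1% to 95.0%, which is fairly described as about 95%. Appendix 8 says enrolment was raised to support a more robust finding from a single pivotal study, which would suit a stricter criterion. The SAP, which takes precedence over the protocol where they differ, might state it. On this view the defect is a missing basis, and replacing 95% with a higher number could remove a correct figure.

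A second argument is that the primary analysis is on the ITT set, planned at 240/160, with missing scores to be handled by imputation. A 98-99% statement for completers could then overstate the power of the actual analysis: with GC4419 non-completers at the Placebo rate it is 97.6%, and harsher assumptions bring it to 95% or below.

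Part of this stands. An unstated basis cannot be excluded, so the sponsor should be free to keep 95% with its basis given. It is also true that Section 12.2 itself prints no alpha, that the figure is qualified as approximate, and that the error is on the safe side. But Appendix 8 gives no alpha, and 0.01 appears nowhere as a test level. The allowances that reach 95% are asymmetric between arms, unstated, and apply to 240/160 rather than to the 216/144 that the power sentence names. The sentence as printed therefore remains wrong at the only level the plan gives.

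**Conclusion.** The point holds. At 216 vs 144, 43% vs 65% and two-sided 0.05, power is 98.6% (98.1% to 98.8% by method), against the stated 95%. The gap is 3.6 points, or a type II error of about 1.4% rather than 5%. It is conservative and minor: the trial is adequately powered on its own assumptions, and the test, the alpha and the enrolment target are unaffected.

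The conclusion rests on two-sided 0.05 being the level behind the power statement. It is the only one the text gives for the primary endpoint. It also takes the stated rates as applying to the completer counts, as Section 12.2 writes them. Whether the separate SAP gives another basis could not be checked.

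**What to change.** In Section 12.2 and in the Statistical Methods part of the synopsis, do one of the following:

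- If the calculation was meant at two-sided 0.05 with 216 and 144 subjects, replace the figure with approximately 98-99% power and print that level and those counts in the same sentence. Optionally add that 95% power is reached at about 65% vs 46%.
- If 95% was computed on another basis, keep it and state the alpha, the method, the analysis set and any assumption about early discontinuations.

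The sponsor can settle which applies from the original sample-size calculation. The cost is wording in two places, with no change in subjects, test or alpha.

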# 12.3. Analysis Populations

Safety and efficacy analyses will be conducted on the ITT population, consisting of all randomized subjects who receive at least one dose of GC4419/Placebo, excluding the 28 subjects whose dosing was affected by the Sponsor's dosing suspension decision. Subjects will be analyzed according to their randomized treatment assignments.

Galera Therapeutics, Inc.

Version: Amendment 4

Randomized subjects who withdraw prior to any dosing will have their reasons for withdrawal noted, and their treatment assignment will remain blinded until the end of the study.

Analyses on other efficacy populations (e.g., "per protocol" population) may be conducted. Such analyses will be specified in the Statistical Analysis Plan for this study.

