## 8.3. GC4419/Placebo Packaging and Labeling

GC4419 and Placebo will be presented in kits of 35 single-use vials, which represent 35 daily doses to be administered IV concurrent with IMRT. To maintain the blind, GC4419, as well as Placebo, will be packaged into amber vials and will appear generally identical; that is, there will be no distinguishing features in or on the packaging that could permit the identification of GC4419 or Placebo.

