# 12.4. Safety Analysis

AEs will be grouped by system organ class, high level term, and preferred term according to the Medical Dictionary for Regulatory Activities (MedDRA) dictionary. Incidence by subject will be tabulated for all treatment-emergent, serious, severe, and treatment-related adverse events. Detailed listings will be provided for all serious adverse events, deaths, and withdrawals due to adverse events.

Laboratory measurements and vital signs will be summarized by treatment group at each of the protocol-specified time points.

Safety parameters will be summarized with descriptive statistics on all subjects who received at least one dose of GC4419/Placebo. Safety analyses will be conducted on the ITT population and the dosing suspension subjects separately.

Further details will be provided in the study's Statistical Analysis Plan.

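### Section 12.3 groups safety by randomized arm, so a subject given the other arm's kit for all or most of the course would have harms reported under a drug not received

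*Combined protocol and SAP*

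**What the plan says.** Section 12.3 opens by covering both kinds of analysis: "Safety and efficacy analyses will be conducted on the ITT population". That population is everyone randomized and dosed, less the 28 subjects caught by the dosing suspension. The grouping rule follows in the same paragraph: "Subjects will be analyzed according to their randomized treatment assignments".

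Section 12.4 adds three relevant statements:

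- Who is counted: "Safety parameters will be summarized with descriptive statistics on all subjects who received at least one dose of GC4419/Placebo".
- How some results are grouped: "Laboratory measurements and vital signs will be summarized by treatment group at each of the protocol-specified time points". Treatment group is not defined as treatment received.
- How the suspension subjects are handled: "Safety analyses will be conducted on the ITT population and the dosing suspension subjects separately". Whether those 28 are grouped by randomized or received treatment is not stated.

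Section 12.4 leaves further detail to the SAP, and Section 12.1 gives the SAP precedence: "In the event of discrepancies between the protocol and the Statistical Analysis Plan, the latter will control the analyses performed". On supply, Section 8.3 says: "GC4419 and Placebo will be presented in kits of 35 single-use vials".

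**The concern.** Analysis by randomized arm is right for efficacy because it preserves the randomized comparison. For safety the usual question is what happened to people who took the drug, so the usual grouping is by treatment received. The two differ only for subjects who were given the wrong product.

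Here the unit of supply makes one error potentially large. A kit holds 35 daily doses, so a single misassigned kit could mean a full course of the other treatment. Section 8.3 makes the two products look alike. Section 8.5 acknowledges that active solution may be slightly tinted, but tells staff who notice this not to discuss it.

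Safety and tolerability is a stated secondary objective (Section 5.1), with adverse events, serious adverse events and laboratory shifts as endpoints (Section 5.2). Under the rule in 12.3, those outcomes in a wrong-kit subject would count against the drug not taken. That pulls the arms together and matters most where a few events carry the signal.

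**Working it through.** The plan gives no figure on this point, so there is none to reproduce. The check has a textual part and an illustrative part.

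**Text.** The grouping sentence in 12.3 follows directly on a sentence that names safety before efficacy, and it carries no exception. In 12.4, the reference to all dosed subjects settles inclusion, not arm. Nothing in the protocol defines an as-treated safety population or says how to count a subject given the wrong kit.

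**Inputs.** From Section 12.2: 240 GC4419 and 160 placebo ITT subjects. Assumed, because the documents give no values: the number swapped for the whole course, the adverse event rates, and the rare-event counts.

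**Common events.** Let *a* of the 240 and *b* of the 160 receive the other product throughout, with true rates pG on GC4419 and pP on placebo. Expected rates by randomized arm are:

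- GC4419: [(240 − a)·pG + a·pP]/240
- Placebo: [(160 − b)·pP + b·pG]/160
- Difference: (pG − pP) × (1 − a/240 − b/160)

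If the same share m of each arm is swapped, the factor is 1 − 2m. With pG = 15% and pP = 5% (true difference 10 points):

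| Swapped | Factor | Difference shown, points |
|---|---|---|
| 0.5% of each arm (about 2 of 400) | 1 − 0.01 = 0.99 | 9.9 |
| 2% of each arm (8 of 400) | 1 − 0.04 = 0.96 | 9.6 |
| 1 per arm | 1 − 1/240 − 1/160 = 0.990 | 9.90 |
| 5 per arm | 1 − 5/240 − 5/160 = 0.948 | 9.48 |
| 12 and 8 (5% of each arm) | 1 − 0.05 − 0.05 = 0.90 | 9.0 |

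Each one-for-one swap costs about 0.1 point. Grouping by treatment received has an expected difference of 10 points throughout.

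**Rare events.** Assume three events, all caused by GC4419, one of them in a placebo-randomized subject who was given GC4419.

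- By randomized arm: 2/240 = 0.83% versus 1/160 = 0.63%, a difference of about 0.2 points.
- By treatment received: 3/241 = 1.24% versus 0/159 = 0%, a difference of about 1.2 points.

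One subject turns a one-sided finding into near parity, although GC4419 still shows the higher rate.

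**Could the direction reverse?** Suppose there is a single drug-caused event and every exposed subject is equally likely to have it. It must fall in a placebo-randomized subject given GC4419 to show as 0/240 versus 1/160.

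- At m = 0.5%: 160 × 0.005 = 0.8 such subjects among 240 − 1.2 + 0.8 = 239.6 exposed, so 0.8/239.6 = 0.3%.
- At m = 2%: 160 × 0.02 = 3.2 among 240 − 4.8 + 3.2 = 238.4, so 3.2/238.4 = 1.3%.

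**The case against.** The strongest reply is that the operative text may lie elsewhere. The SAP overrides the protocol, Section 12.4 defers to it for safety detail, and Appendix 8 says Amendment 4 was aligned with a final SAP. That SAP may already define an as-treated set. This stands: the finding concerns the protocol's wording, and it is not established that the safety tables will be built this way. It does not remove the point, because such a SAP would contradict 12.3 and the two would still need aligning.

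Second, the harm is hypothetical. No misdosed subject is reported. Assignment runs through an interactive system (Section 8.2), dispensing records tie container or lot number to subject, and the monitor verifies them (Section 8.7). These controls make a wrong kit less likely to pass unnoticed for a whole course. They do not say in which arm to count the subject if it happens.

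Third, safety is descriptive, common-event rates barely move, and Section 12.4 promises listings of serious events, deaths and withdrawals due to adverse events. All true, although nothing says those listings will show treatment received.

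A reader might also infer that harm in any misdosed subject goes to the wrong drug. That is clear only for a wrong kit, or most of a course. With one wrong vial among 35, most exposure still matches the randomized arm.

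**Conclusion.** The point holds in a limited form. As written, 12.3 applies randomized grouping to safety and 12.4 does not undo it. A subject treated for all or most of the course from the other arm's kit would be reported under a drug not received.

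The size depends on assumptions. Under an assumed swap of 0.5% to 2% per arm, a 10-point difference in a common event shows as 9.9 to 9.6, which is small. The practical exposure is in rare events, where one subject can blur a signal (2/240 versus 1/160, against 3/241 versus 0/159).

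A reader might go further and conclude that the rule is likely to reverse a safety signal, or that the trial's safety results are already compromised. The documents support neither. Reversal in the single-event case needs a coincidence of roughly 0.3% to 1.3% under the same assumptions, and no misdosing is on record. The conclusion also rests on no SAP provision already curing the rule.

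**What to change.** First check the SAP. If it defines an as-treated safety set, align 12.3 and 12.4 with it. If not, amend both sections before unblinding, since choosing the rule once discordant subjects are known by arm would be open to challenge:

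- Keep randomized assignment for efficacy.
- Group safety by treatment actually received, taken from the dosing and accountability records in Section 8.7. The PK samples sought from all subjects (Section 10.4.1) can help confirm exposure.
- Apply the same grouping to the 28 dosing-suspension subjects, still shown separately.
- State a rule for mixed exposure in advance. For example, a placebo subject with any GC4419 dose is counted under GC4419 only for events starting on or after that dose, or is shown separately. A bare any-dose rule is not enough: events are collected from randomization (Section 11.2.2), so one wrong vial would move a placebo subject's earlier events to GC4419.
- List every subject whose received and randomized treatments differ.

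The cost is one derived variable and one listing. Efficacy, alpha and power are unaffected, and the tables do not change if nobody was misdosed.
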